## ABSTRACT

Glioblastoma (GBM) is the most common primary malignant brain tumor in adults. The current standard of care is maximal safe resection followed by radiation therapy (RT) with concurrent and adjuvant temozolomide (TMZ) chemotherapy. Despite this aggressive management, GBMs invariably progress resulting in significant morbidity and mortality for patients. Overall, the single most effective adjuvant treatment for this disease is RT. Patients are generally treated with focal radiation to a dose of 60 Gy to the highest risk regions and a lower dose (45-54 Gy) to lower risk regions. However, despite this therapy, tumor will generally regrow within the high dose volume suggesting that GBMs are relatively radioresistant and that increasing radiation doses may be beneficial for patients with this tumor. However, dose escalation studies that treat beyond the 60 Gy standard have not been shown, to date, to improve patient outcomes. It is important to note that most of these dose escalation studies were conducted in the pre-temozolomide era. Interestingly, one study utilizing proton therapy with doses up to 90 cobalt gray equivalent (CGE) did change the pattern of recurrence from within the high dose volume to the margins of this region, particularly where doses fall below 70 CGE. This result suggests that current MRI-based approaches for defining tumor volume/margin may not fully identify all regions at highest risk for recurrence and that better identification of the high risk regions will now allow realization of the benefits of dose escalation in this disease. Indiscriminate increases in treatment margin may allow delivery of dose-escalated radiation to the needed region(s) at the cost of irradiating wide areas of the brain with these higher doses significantly increasing the likelihood of unacceptable morbidities. Thus, improved definition of the regions at highest risk for recurrence will allow dose escalation to be targeted to a more limited volume that would be better tolerated by patients.

Currently, MRI using T1-weighted ( $T_{1w}$ ) post-contrast and  $T_2$ /FLAIR sequences is used to define treatment volumes for radiation planning; however, these sequences may not identify all regions in the brain at highest risk for tumor recurrence. Proton magnetic resonance spectroscopic imaging (MRSI) is an alternative modality that is able to map certain metabolite levels within the brain. This may allow for more accurate characterization of regions with significant tumor involvement than would be achievable with conventional MRIs. Several reports demonstrate that a high choline (Cho) to N-acetyl aspartate (NAA) ratio (Cho/NAA) correlates with areas of high tumor cell density and, after treatment, areas of tumor recurrence. However, MRSI is not widely used in clinical practice due to relatively low resolution, long acquisition time, and inefficient data analysis and visualization in commercially available packages. The first two limitations have now been overcome with state-of-the-art technology utilizing EPSI (echo planar spectroscopic imaging) with GRAPPA (parallel imaging) for the spectroscopic imaging. High resolution, three dimensional (3D), whole brain metabolite maps can now be obtained in relatively short (12-15 minute) scan times and in a form that can be registered with other conventional MR images by utilizing an advanced analysis and visualization tool. We have now termed this advanced imaging modality spectroscopic MRI (sMRI). Based on a recently completed early phase clinical study sponsored by NCI, "combining high resolution MRSI with 5-ALA to improve complete resection in GBM surgery" (NCI R21 CA186169; Emory IRB00051663), we learned that sMRI Cho/NAA showed significant correlations with tumor cell density in histological results ( $p = 0.82$ ,  $p < 0.001$ ). Based on early data from the control arm of on-going clinical study, "Quantitative MRSI to predict early response to histone deacetylase inhibitor therapy in new GBM management" (NCI U01 CA172027; Emory IRB00055973) and an institutional study "MRSI in the treatment planning and assessment of glioblastoma" (Emory IRB0006545), sMRI metabolic abnormalities predated contrast-enhancement at sites of tumor recurrence and exhibited an inverse relationship with progression-free survival (Cordova et al. This Neuro-Oncology article is enclosed in Appendix).

We believe that the combination of sMRI and conventional MRI scans can be used to guide radiation therapy target definition and dose-escalated treatment planning, significantly improving outcomes for patients with this highly aggressive brain tumor.

## STUDY SCHEMA

## 1.0 INTRODUCTION AND BACKGROUND

Glioblastomas (GBMs) are aggressive primary brain tumors of astrocytic origin. Approximately ten thousand new cases are diagnosed each year in the U.S., making it the most common primary malignant brain tumor in adults. While radiation therapy (RT) has long been used in the treatment of GBMs and will delay their progression, it generally will not control these tumors long term. Incremental progress has been made in the management of GBMs, most recently with the addition of temozolomide (TMZ) chemotherapy to RT; however, outcomes remain poor, with a median survival of only 14-15 months [1, 2]. Recurrence is largely due to the inherently infiltrative nature of GBM, with tumor cells migrating to regions distant from the central contrast-enhancing regions. Because of this, regions of nonenhancing signal abnormality on fluid-attenuated inversion recovery (FLAIR) or T2-weighted ( $T_{2w}$ ) images are covered in a typical RT treatment plan, albeit with moderate doses. However,  $T_{2w}$ /FLAIR is not tumor-specific due to difficulties in differentiating nonenhancing tumor from other causes of increased FLAIR or T2 signal (e.g. radiation effects, ischemic injury, edema, and infection) [3, 4]. T1-weighted -contrast-enhancing ( $T_{1w}$ -CE) MRI displays the leaky neovasculature associated with these tumors, indicating well-perfused tumor lesions with excellent oxygen and chemotherapeutic drug delivery. Despite the constant effort of tumor cells to recruit new blood vessels (neoangiogenesis), there is a significant gradient of oxygen. Hypoxia occurs in tumors 100  $\mu$ m away from the blood supply, and tends to be widespread in GBMs. The viable hypoxic cells existing in solid tumors are associated with the failure of radiation and certain chemotherapy regimens [5]. Obviously, IV contrast agents cannot effectively reach all the tumor cells beyond the contrast-enhancing border; therefore, it is unreasonable to use conventional  $T_{1w}$ -CE MRI alone as the basis for RT treatment planning. Newer imaging methods are desperately needed to identify the actively proliferating tumor beyond the  $T_{1w}$ -CE area. This could potentially make a significant impact on improving tumor control.

Based on retrospective analysis of successive Brain Tumor Study Group trials, a fractionated dose of 60 Gy was determined to be optimal for GBMs [6]. A typical RT dosing regimen for the treatment of GBM involves treating a wide volume, including nonenhancing  $T_{2w}$ /FLAIR-hyperintense regions with margin, to a moderate dose (45-54 Gy), followed by a boost to the resection cavity plus any residual  $T_{1w}$ -CE abnormality with margin to a higher dose (60 Gy). A study using proton therapy for GBM found that patients not only tolerated doses up to 90 cobalt-gray equivalent (CGE), but also started to display a change in the pattern of recurrence with nearly all failures in regions receiving < 70 CGE [7]. Of note, TMZ was not used for this study. This result suggests that tumoricidal doses (in the 70+ Gy range) may have finally been achieved, with marginal failures now being due to growth of disease that had infiltrated into brain surrounding the initial contrast-enhancing portion of the tumor. This study also suggests that better definition of the brain volume most at risk for tumor recurrence may allow better targeting of these regions with higher doses leading to improved local control and overall patient outcomes. Combining RT dose escalation with concurrent/adjuvant TMZ may produce more toxicities, especially since the incidence of pseudoprogression after concurrent RT/TMZ is significantly higher than after RT alone. Pseudoprogression is the phenomenon where an early increase in volume of contrast enhancement is seen following treatment with RT/TMZ (usually within 3 months post-RT). This effect is indistinguishable from early true tumor progression by standard MR imaging, and is generally only distinguished by serial imaging over time, when this change either stabilizes/improves (pseudoprogression) or continues to worsen (true progression) without alterations in the therapy. Brandes et al. have reported that the overall incidence of pseudoprogression is on the order of 30% in patients treated with the Stupp regimen [8]; therefore, it follows that TMZ may also alter tolerance to dose-escalated RT. This concern has been somewhat allayed by Tsien et al. with their report that TMZ could be safely paired with dose-escalated intensity modulated RT [9]. Of note, no late grade III or greater CNS toxicities were seen with doses up to 75 Gy, and for doses above 75 Gy (7 pts at 78 Gy and 9 pts at 81 Gy), only 3 patients developed  $\geq$  grade III late CNS toxicities. Thus, it appears that dose-escalated RT may be safely paired with TMZ. Since previous results also suggest that very high radiation doses (70+ Gy range) shift the pattern of recurrence to the margins of the high dose irradiation zone [7], there is now a greater premium on defining further areas that may be at increased risk of recurrence that can potentially be boosted by these higher doses.

Currently, GBMs are imaged with conventional MRI sequences, including  $T_{2w}$ , FLAIR, and pre- and post-contrast  $T_{1w}$  sequences, and some advanced MRI techniques, including diffusion-weighted imaging (DWI), and dynamic susceptibility contrast (DSC) and/or dynamic contrast-enhanced (DCE) perfusion-weighted imaging (PWI). DWI and PWI MRIs have been used to follow response of GBMs to therapy, but have not proven particularly useful for RT planning [10-12]. Similarly, diffusion tensor imaging (DTI), a MR technique that describes the movement of water molecules using metrics, such as mean diffusivity (MD), and fractional anisotropy (FA), which represent the magnitude and directionality of water diffusion, respectively [13, 14], did not have value for predicting recurrences outside the high dose irradiated regions of brain when analyzing a cohort of GBM patients treated at the University of Pennsylvania ([name], personal communications). Overall, the most common advanced MRI techniques have proven disappointing at identifying high risk regions that can be better targeted with radiation.

Proton magnetic resonance spectroscopic imaging (MRSI), which can characterize regions of brain based on levels of various metabolites and other substances, is a candidate imaging modality for defining high risk regions that are not identified by standard MRI. Metabolites that can be evaluated include choline (Cho), a peak reflecting cell membrane synthesis that is elevated in highly proliferating, non-necrotic gliomas; creatine (Cr), an energy metabolite; and N-acetyl aspartate (NAA), a healthy neuronal biomarker. Early studies established that the MR spectra of GBMs differ significantly from normal brain, with increased levels of Cho, and decreased levels of NAA [14, 15]. MRSI has even been evaluated as a guide for RT planning when registered with the conventional MRI scans and treatment-planning CT scans [16-19]. Park et al. correlated the pattern of recurrence after RT with pre-treatment MRSI findings and noted that 8 of 9 patients with a growing enhancing lesion post-RT had recurrence in regions with high Cho/NAA [20]. Stadlbauer et al. demonstrated in gliomas that MRSI-derived Cho/NAA ratios frequently identified regions at higher risk of tumor beyond the  $T_{2w}$  signal abnormalities, and concluded that MRSI may be useful for delineating infiltrating nonenhancing tumor (beyond contrast enhancing tumor), which has clear implications for therapeutic planning [21, 22]. These previous studies have shown that MRSI can help identify GBMs, and potentially provide guidance for RT management. However, with poor resolution and limited field-of-views among a host of other difficulties, it has not been possible to exploit current clinical implementations of MRSI for use in RT treatment planning.

We have been using an advanced spectroscopic technique we have termed spectroscopic MRI (sMRI) which combines advanced technologies, such as 3D echo-planar spectroscopic imaging (EPSI), parallel acquisition (GRAPPA), and elliptical k-space encoding, with a 32-channel head coil. This acquisition obtains metabolite maps over approximately 65% of the brain coverage with high resolution in 15 minutes. This sMRI sequence was developed 10 years ago by [name] (University of Miami) and has been adapted in multiple clinical studies by numerous investigators in the world. We have been using sMRI in various clinical studies at Emory. Based on a recently completed early phase clinical study sponsored by NCI, "combining high resolution MRSI with 5-ALA to improve complete resection in GBM surgery" (IRB00051663), we learned that sMRI Cho/NAA showed significant correlations with tumor cell density in histological results ( $p = 0.82$ ,  $p < 0.001$ ). Based on early data from the control arm of on-going clinical study, "Quantitative MRSI to predict early response to SAHA therapy in new GBM management" (IRB00055973) and an institutional study "MRSI in the treatment planning and assessment of glioblastoma" (IRB0006545), sMRI Cho/NAA metabolite ratio map before RT treatment initiation matched well with contrast-enhancement at sites of tumor recurrence and exhibited an inverse relationship with progression-free survival (Cordova et al. This Neuro-Oncology article is enclosed in Appendix). Here, we will use our high-resolution, volumetric sMRI combined with standard MRIs that are routinely performed in the clinic for focal radiotherapy planning with escalated doses to select regions for the potential benefit of newly-diagnosed GBM patients.

## 2.0 OBJECTIVES

Our main goal is to establish the use of sMRI in addition to standard contrasted MRIs to guide dose-escalated radiation therapy for newly-diagnosed GBM patients. We have demonstrated that sMRI

has reached a level of technical development and validation where it is now feasible to use it for mapping regions of brain at high risk for tumor recurrence that may not have otherwise been appreciated by contrast-enhanced MRIs. In addition, the safety of this dose-escalated treatment approach will need to be demonstrated before it can be more widely adopted. Finally, we will also assess the efficacy of selectively targeting RT dose escalation with sMRI guidance in comparison to historical controls.

## 2.1 Primary Objectives

- 2.1.1 To determine the feasibility of using sMRI to guide dose-escalated RT for newly-diagnosed GBMs.
- 2.1.2 To determine the safety of using sMRI to guide dose-escalated RT for newly-diagnosed GBMs.

## 2.2 Secondary Objectives

- 2.2.1 To determine whether the progression free survival at 1 year with sMRI-guided, dose-escalated RT is improved for newly-diagnosed GBMs.

## 2.3 Exploratory Objectives

- 2.3.1 To determine whether sMRI-guided, dose-escalated RT increases the overall survival of patients with newly-diagnosed GBMs.
- 2.3.2 To determine whether sMRI data obtained after initiation of therapy (at 2 weeks after RT/TMZ start and prior to cycle 1 and 5 of adjuvant TMZ) will provide early evidence of GBM progression not seen on standard MRIs.
- 2.3.3 To determine whether performance on neurocognitive and quality-of-life (QOL) assessments in newly-diagnosed GBM patients treated with sMRI-guided, dose-escalated RT differ from historical controls.

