## 7.0 STUDY EVALUATIONS

### 7.1 Summary of Active Monitoring Schedule

Tests and procedures	Pre-reg	≤21 days prior to start of therapy	Chemoradiation (RT+TMZ, 6 weeks)						Adjuvant TMZ Cycles 1-12  ≤7 days before each cycle	After completion of adjuvant TMZ
			1	2	3	4	5	6		
Path diagnosis	X									
H&P, weight, KPS		X		X 		X 		X 	X	X 
Height		X								
Neuro exam		X		X 		X 		X 	X	X 
Adverse event assessment		X	X 	X 	X 	X 	X 	X 	X	X 
Rad Onc consult	X 									
Neuro Onc consult	X 									
CBC w/diff		X	X 	X 	X 	X 	X 	X 	X	
CMP 		X	X 	X 	X 	X 	X 	X 	X	
MRI w/contrast 		X							X 	X 
sMRI (Research)		X			X 					
Steroid/anti-Sz/chemo med documentation		X	X 	X 	X 	X 	X 	X 	X	
Neurocognitive and QOL assessments (Research)		X							X 	X 
Pregnancy test		X 								

-  Comprehensive Metabolic Panel (CMP) - Sodium, potassium, bicarbonate, chloride, BUN, creatinine, calcium, glucose, total bilirubin, SGOT (AST), SGPT (ALT), alkaline phosphatase, albumin, total protein (Standard care). The frequency of CMP will be up to the treating physician's discretion.
-  Standard diagnostic brain MRI w/ & w/o contrast.
-  Either Rad Onc or Neuro Onc consultation needs to be completed at pre-registration. The other consultation can be completed  $\leq$  21 days before initiation of therapy. (Standard care)
-  To be completed only in women of childbearing potential. Test obtained  $\leq$  21 days prior to registration. May use a test result obtained for other clinically warranted indications if the test date is within the above time window. (Standard care)
-  To be assessed during chemoradiation. (Standard care)
-  Document steroids, anti-seizure, and temozolamide meds weekly during cycle 1. (Standard care)
-  To be performed every other week starting on week 2 of chemoradiation. (Standard care)

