-  sMRI should be performed during the 3rd week of chemoradiation (after 10 fractions up to 15 fractions, or prior to receiving the 16th fraction). ([Research](#))
-  TMZ cycles will be determined at treating physician's discretion. (Standard care)
-  Standard diagnostic brain MRI w/ & w/o contrast to be completed  $\leq$  7 days prior to starting each odd number cycles. (Standard care)
-  To be performed every 6 months ( $\pm$  1 month) after pre-cycle 2 assessment until progression (will attempt to obtain final assessment only if date of progression is  $>$  3 months from previous assessment) or until approximately 2 years after pre-cycle 2 assessment (maximum of 4 additional assessments). ([Research activity](#))
-  Follow-ups and standard diagnostic brain MRI w/ & w/o contrast to be completed 1 month ( $\pm$  2 weeks) after completion of adjuvant TMZ chemotherapy and then every 3 months ( $\pm$  2 weeks) (until approximately 2 years after RT). Subsequent followups/MRIs will be determined by treating physician. (Standard care)

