## 11.0 TREATMENT EVALUATION

## 11.1 Objectives – (see section 2.1-3)

## 11.2 Imaging assessment

**11.2.1 Conventional MRI scans (Standard care):** Diagnostic MRI scans with and without contrast will be utilized to assess for response.

**11.2.2 sMRI (Research, 2 scans at week 0 (before treatment) and week 2):** 3-D whole brain MR spectroscopic imaging sequence (EPSI/GRAPPA) and the analysis program MIDAS (Metabolic Imaging Data Analysis System) were developed by [name] (scientific PI of U of Miami) in 2006 [31-42]. The scan will be done in 3T Siemens MR scanner (TIM/TRIO, Prisma, Skyra) or equivalent. Metabolite maps and their ratio maps will be calculated in MIDAS. Due to some degree of variability of Cho/NAA ratio between subjects, we will use the signal from contralateral normal white matter for normalization. We will use a web-based sMRI clinical interface to extract information from MIDAS to visualize the metabolite maps for efficient clinical workflow of the MIDAS results for busy clinicians and non-MRS experts. In addition, this web-based tool allows effective data sharing among imaging scientists and clinicians for consultation and storage of de-identified data sets (this sMRI clinical interface has been used at Emory (NCI U01 CA172027 & NCI R21 NS100244; Emory IRB00055973). sMRI studies will be obtained at the schedule outlined in section 7.1.

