Because of difficulties in the interpretation of pseudo-progression on MRI, the first three post-RT/TMZ scans should NOT be used to declare progression. Progressive worsening on subsequent imaging studies usually distinguishes true progression from pseudoprogression. In particular, DSC perfusion imaging may be helpful at distinguishing true and pseudoprogression. If the rCBV map does not show evidence of increased perfusion in regions with increasing contrast-enhanced lesion(s), then pseudoprogression is favored and patient may be maintained on study. Subsequent increases up to 6 months post-RT will be evaluated on a case-by-case at a multi-disciplinary tumor board of the respective institution to assist in making a determination regarding true versus pseudoprogression and whether pathologic sampling would be beneficial. The date of progression will be backdated to when the changes were first observed in the case that the patient is later determined to have true progression.

**11.3.3.5 Regressive Disease (REGR):** (Evaluable disease only) Unequivocal reduction in extent of contrast as compared to baseline-enhancement or a decrease in mass effect as agreed upon independently by primary physician and quality control physicians; no new lesions.

**11.3.3.6 Unknown:** Progression has not been documented and one or more measurable sites have not been assessed.

**11.4 Best Response:** This will be calculated from the sequence of objective statuses. For patients with all disease sites assessed every evaluation period, the best response will be defined as the best objective status as measured according to section 11.5.

**11.5 Neurological Exam:** Although not used for determining response, it is useful to evaluate improvement in the neurologic exam, as compared with the baseline assessment, that should coincide with objective measurement of tumor size.

NEURO EXAM STATUS (compared to pre-treatment exam)	
Better	Must be on stable or decreasing dose of steroids
Same	Failure to qualify for better or worse
Worse	Include patients requiring increasing steroid doses to remain stable

**11.6 Performance Status:** Patients will be graded according to Karnofsky Performance Status (see Appendix 3).

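### The only sMRI scheduled after treatment starts has no standard MRI near it, so objective 2.3.2 cannot show progression that standard MRI misses, and 2.3.2 and 14.3.2 name sMRIs that the schedule omits

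*Combined protocol and SAP*

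**What the plan says.** Objective 2.3.2 asks whether sMRI obtained after therapy begins "will provide early evidence of GBM progression not seen on standard MRIs". The same sentence lists the scans: "at 2 weeks after RT/TMZ start and prior to cycle 1 and 5 of adjuvant TMZ". Section 14.3.2 repeats both the question and the list. It then plans to examine whether changes in sMRI parameters forecast recurrence, for the patient as a whole and voxel by voxel.

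The schedule differs. Section 11.2.2 is headed "sMRI (Research, 2 scans at week 0 (before treatment) and week 2". The sMRI row of Table 7.1 has entries only before therapy and in chemoradiation week 3. Footnote 8 sets the window for the second scan: "after 10 fractions up to 15 fractions", and in any case before fraction 16. There is no sMRI entry in the adjuvant or follow-up columns.

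The contrast MRI row of Table 7.1 has a baseline entry and nothing in weeks 1 to 6. In the adjuvant phase, footnote 10 applies: "Standard diagnostic brain MRI w/ & w/o contrast to be completed" within 7 days before each odd-numbered cycle. Section 4.3 says that the sMRI involves no contrast injection.

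On progression, section 11.3.3.4 says that "the first three post-RT/TMZ scans should NOT be used to declare progression". The same section, and the PFS definition in 11.9, date confirmed progression back to the first scan that showed the change.

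**The concern.** The question in 2.3.2 compares two imaging methods. To say that sMRI showed something standard MRI did not, a patient needs both at about the same time, or the analysis must allow for what standard imaging already showed. The schedule provides no such pair after treatment starts. The week-3 sMRI has no standard MRI beside it, and because it is done without contrast it cannot serve as its own comparator. The pre-cycle 1 and pre-cycle 5 sMRIs, which would fall beside standard MRIs, are named in the objective but not scheduled.

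What is at stake is how an exploratory result is read. A week-3 sMRI change in a patient who later progresses will precede the next scheduled MRI because of the visit calendar. Section 14.6 links metabolite changes during RT to possible adaptive radiotherapy, so an apparent head start could be carried into later work as evidence of added value.

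**Working it through.** The plan gives no sample size, power or lead-time figure for this objective, so there is none to reproduce. The check rebuilds the calendar, counting day 1 as the first fraction and assuming no delays.

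**Inputs**
- 30 weekday fractions, starting Monday to Thursday (8.1.1, 8.1.7.1, 8.2).
- sMRI after fraction 10 and before fraction 16 (7.1, footnote 8).
- Break from RT to cycle 1 of 28 to 42 days. Section 8.2 gives 4–6 weeks in one line and 4–5 in another; the wider range is used.
- 28-day adjuvant cycles (8.2).
- Standard MRI 0 to 7 days before odd cycles (7.1, footnote 10); baseline MRI within 21 days before therapy (7.1).

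**Step 1: week-3 sMRI.** With a Monday start, fraction 10 is on day 12, fraction 16 on day 22 and the last fraction on day 40. With a Tuesday to Thursday start, these are days 14, 22 and 42. The sMRI window is therefore day 12 to 22.

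**Step 2: next standard MRI.** Date = last fraction + break − (0 to 7 days). Earliest: 40 + 28 − 7 = day 61. Latest: 42 + 42 = day 84.

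**Step 3: gap to the next standard MRI.** Shortest: 61 − 22 = 39 days. Longest: 84 − 14 = 70 days (a Monday start gives 82 − 12 = 70). If the break is at most 5 weeks, the longest is 77 − 14 = 63 days. Looking back, the baseline MRI is 12 − 1 = 11 days to (22 − 1) + 21 = 42 days earlier.

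**Step 4: fourth post-RT MRI.** This is the pre-cycle 7 scan, 6 × 28 = 168 days after the pre-cycle 1 scan: day 61 + 168 = 229 to 84 + 168 = 252. Its gap from the sMRI is 39 + 168 = 207 to 70 + 168 = 238 days.

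**Step 5: which gap governs the recorded date.** The bar on the first three post-RT scans delays the declaration to the fourth. Backdating can then move the recorded date as far back as the pre-cycle 1 scan. The separation fixed by the schedule is thus 39–70 days, not 207–238.

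**Step 6: scans named against scans scheduled.**

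| sMRI after treatment starts | 2.3.2 and 14.3.2 | 7.1 and 11.2.2 | Standard MRI beside it |
|---|---|---|---|
| Week 2–3 of chemoradiation | named | scheduled | none |
| Before cycle 1 | named | not scheduled | first post-RT scan |
| Before cycle 5 | named | not scheduled | third post-RT scan |

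Three are named and one is scheduled. The two missing scans would sit beside MRIs that 11.3.3.4 says should not be used to declare progression.

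**Step 7: events available to a model.** Section 14.5 gives 1-year PFS from 30% (historical) to 60% (hoped for). With 30 patients and complete follow-up, that is 30 × 0.40 = 12 to 30 × 0.70 = 21 events by one year. Four covariates would have 12/4 = 3 to 21/4 ≈ 5 events each. Two or three covariates would have 12/3 = 4 to 21/2 = 10.5.

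**The case against.** The strongest reply is that 14.3.2 plans a prediction analysis, not a race between two scanners. sMRI appears nowhere in the response criteria, cannot declare progression, and has no lead-time count attached to it. Whether week-3 change relates to later recurrence can be tested and can come out negative. That stands. A reader might infer that the objective's answer is built in and nothing is tested, or that the trial will report a lead time. The documents support neither. What they leave untestable is the comparison with standard MRI that the objective states.

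A reader might also infer that the bar on the first three post-RT scans creates a lead of about 30 weeks. It does not: backdating in 11.3.3.4 and 11.9 means that the bar delays the declaration but does not itself create the recorded gap. Progressive disease can also be called on clinical worsening, without that imaging restriction.

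A further reply is that the pre-cycle 1 and 5 sMRIs would supply the missing pairs. They would supply same-time images, but only beside MRIs barred from declaring progression, and no sMRI criterion or paired comparison is defined. Restoring them would not settle the matter without such a rule.

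Finally, the objective is exploratory and the sample small. Both points are correct. They limit the weight of the concern and the size of any model.

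**Conclusion.** The concern holds in a limited form. As scheduled, the one sMRI after treatment starts has no same-time standard MRI; the nearest later one is 39–70 days away. Neither superiority to standard MRI nor a lead over it can be assessed from these data, while an association between week-3 change and later recurrence can be. Sections 2.3.2 and 14.3.2 also contradict 7.1 and 11.2.2 on which sMRIs are done.

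The figures assume no treatment delays, scheduled scans only, and the pre-cycle 1 MRI as the first after RT. A longer rest period, which 8.2 allows, would widen the gap. An unscheduled MRI could narrow it in individual patients, but no analysis uses one as a comparator. Feasibility, safety and PFS conclusions are unaffected. The change is worth making because it is cheap and alters what may be claimed.

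**What to change.** 1. Reconcile 2.3.2 and 14.3.2 with 7.1 and 11.2.2 on which sMRIs are done after treatment starts. If the pre-cycle 1 and 5 scans are kept, define how a paired sMRI and standard MRI will be read, given that those MRIs may not be used to declare progression.
2. For the week-3 scan, reword 2.3.2 and 14.3.2 to ask whether the week-3 change in Cho/NAA volume adds to baseline standard imaging in predicting PFS. Count PFS from a week-3 landmark in patients still event-free. Make no lead-time claim and no claim that the finding was absent on standard MRI.
3. Keep the model small or penalised: for example, change in Cho/NAA volume plus one or two baseline imaging volumes. Report it as an exploratory estimate with a patient-level confidence interval.

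The cost is a wording change and one model. No scan is added. The baseline images already feed the contours in 8.1.4, and images and structures are stored centrally under 15.2. Because GTV3 merges the Cho/NAA region with residual enhancement, and GTV1 includes GTV2 and GTV3, the component volumes would need to be extracted separately. The downside is a more modest claim and, with about 12–21 events by one year, an imprecise estimate.
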